with a high percentage of African Americans from urban and rural areas of Louisiana will be randomized to either 1) intervention or 2) usual care. The sample will include up to 850 patients (18 clinics, 47 patients/clinic). Justification of Sample Size. The sample size calculations were based on the Louisiana Obese Subjects Study (LOSS), a pragmatic clinical trial conducted by Pennington Biomedical comparing intensive medical intervention for obesity versus usual care.⁴ According to the 2013 Obesity Guidelines, as little as 3-5% weight loss is likely to result in clinically meaningful health outcomes.³ Thus, the sample size calculations assume that the study is powered to detect a mean weight loss in the intervention arm of 3.5% at 2 y, relative to usual care, in race- and sex-specific subgroups. We are targeting a mean weight loss of >5% which we anticipate to be 3.5% more than usual care. Both the total and relative weight loss meet accepted levels of clinical significance. Power calculations used a nominal 0.05 significance level with a two-tailed test with minimal power of 80%. Based on LOSS, the standard deviation for weight change for patients nested within clinics was 8.4%. For the subgroup analysis, a net sample size of 92 patients/arm is sufficient for detecting a 3.5% weight loss with 80% power with patient-level randomization. After accounting for the design effect, at least 134 patients per arm are required to realize 80% power in a trial randomized at the clinic level. Allowing for 30% attrition, at least 192 patients per arm are needed with a total enrollment of 384 patients per subgroup. Inclusion/Exclusion Criteria. Given that this is a pragmatic trial, the inclusion criteria are broad and include having a BMI 30 to 50 kg/m², and an age 20 to 75 years. Women will be required to be non-pregnant and agree to avoid pregnancy during the study. Exclusion criteria include a history of major depression, suicidal behavior or eating disorder, hospitalization for mental disorder or substance abuse in the previous year, active cancer, cardiovascular or cerebrovascular disease event in the past year, heart failure, and current use of weight loss medications or recent weight loss. Outcomes. The primary outcome is percent change in body weight from baseline. Secondary outcomes include change in quality of life, functional capacity, satisfaction with medical care, and obesity co-morbidities (hypertension, dyslipidemia, insulin resistance, urinary incontinence and respiratory problems such as sleep apnea). The secondary outcomes were selected based on the prior experience of the investigators working with obese patients, and they should be considered preliminary, as they could change based on our planned patient focus groups. Analytic Methods. Analyses will be performed on an intent-to-treat basis. For continuous outcomes, a linear mixed model for repeated measures over time will be used, including the fixed effects of intervention, time, and their 2-factor interactions, with age, sex and clinic as covariates. For dichotomous outcomes, a generalized linear mixed model with a logit link will be applied using the same modeling approach. Estimated within-group changes between baseline and 6 to 24 months will be estimated and compared using contrasts within the mixed models. Baseline outcomes will further be included in the models as covariates to determine the change in outcome from baseline. The study design will also allow for analysis of clinic-level characteristics that are associated with better outcomes. Anticipated Effect Size. Weight loss in the lifestyle intervention arm of Look Ahead was 6.4% at 2 y, compared to 1.1% in the education arm.⁵ The original Diabetes Prevention Program (DPP) intensive lifestyle intervention produced a weight loss of 5.8% at 2 y⁶, and this effect has been replicated in a DPP adaptation for deployment through the YMCA, with an initial weight loss of 6% in the intervention versus 2% in control group at 6 months⁷; a reduction which was maintained in the intervention arm at 2 y.⁸ Further, the 2 y results from LOSS showed between 4.9% (baseline carried forward analysis) to 9.6% (completers only) weight loss in the intensive medical intervention arm, compared to 0.4% for usual care.⁴ Thus, based on these prior studies, and the delivery of the proposed intervention in a primary care setting, we anticipate achieving at least a 3.5% weight loss differential between intervention and usual care. Treatment Arms. Trained coaches under provider supervision will deliver the active intervention - a comprehensive, "high-intensity" program, as recommended

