A variety of approaches will be used to retain patients. Based on our experience, we understand the importance of creating a pleasant clinic environment and friendly and welcoming staff presence. We are also very clear from the initial screening session onward about what we expect from patients and what they can expect from us, as keeping patients well informed enhances adherence to the intervention and test schedules. Further, we will provide small gifts to patients including hats, umbrellas, coffee cups, etc., with the study logo, which has improved retention in our previous studies. Finally, a total of \$375/patient is budgeted for incentives related to the provision of outcome measures. All patients will be paid at the completion of each assessment visit (\$75 at each of baseline, 6, 12, 18 and 24 months).

9. Randomization and Blinding

Randomization

This is a cluster-randomized trial, and enrolled patients at a given clinic will receive the intervention assigned to their clinic. A pool of 18 clinics will be randomized to either 1) usual care or 2) intervention, after stratification by health system. Stratification by health system is necessary to ensure adequate local staffing of clinics assigned to the intervention arm, representation from all regions of the state and types of health systems in both arms of the trial.

Blinding

Given that this trial is randomized at the clinic level and the interventions are very distinct, PROPEL patients will know their group assignment, as will clinic staff and health educators that are involved in delivering the intervention. However, every effort will be made to blind staff involved in data collection to the clinic randomization, and all intervention staff will be blinded to the patients' official study measurements.

10. Intervention Methods

Overview of Intervention Arms

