The focus of the PCORI Funding Announcement under which this study was funded is on obesity reduction in adults therefore the patients in this study are mainly adults (20 - 75 y of age). The treatment of childhood obesity is beyond the scope of this intervention.

15. Power and Sample Size

The sample size calculations for PROPEL were based on LOSS, a pragmatic clinical trial conducted by Pennington Biomedical in eight primary care clinics across the state of Louisiana comparing intensive medical intervention for obesity versus usual care.⁴ According to the 2013 *AHA/ACC/TOS Obesity Guidelines*, as little as 3-5% weight loss is likely to result in clinically meaningful health outcomes.²⁹ The calculations assume that the study will be powered to detect a mean weight loss in the intervention arm of 3.5% at 2 y, relative to usual care, in race- and sex-specific subgroups. We are targeting a mean weight loss of >5% which we anticipate to be 3.5% more than usual care. Both the total and relative weight loss meet currently accepted levels of clinical significance.

Power calculations used a nominal 0.05 significance level with a two-tailed test with minimal power of 80%. Based on the LOSS study, the standard deviation for weight change for patients nested within clinics was 8.4%. For the subgroup analysis, a net sample size of 184 patients (92/arm) is sufficient for detecting a 3.5% weight loss with 80% power when randomization is performed at the patient level. After accounting for the design effect, at least 134 patients per arm are required to realize 80% power in a trial randomized at the clinic level. A previous study in primary care (PROACTIVE) had 20% attrition over 24 months. However, given the challenges of working with a clinic population across an entire state, we have allowed for a conservative estimate of 30% attrition for this trial. Thus, allowing for 30% attrition, at least 192 patients per arm are needed with a total (2 arms) enrollment of at least 384 patients per subgroup analyses.

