Based on data from the patient population served by Louisiana safety net hospitals⁸² and Federally Qualified Health Centers in Louisiana which is approximately 50% African American and 50% female, this translates into a total sample size of at least 768 patients, which will provide at least 97% power to detect a mean weight loss in the intervention arm of 3.5% at 2 y, relative to usual care in the total sample. To account for the increased rate of attrition in Federally Qualified Health Centers, up to 850 participants (425 patients per arm / 47 patients per clinic / 18 clinics) will be enrolled. Although Hispanics will be included in the trial, the low Hispanic population in LA (4%)²¹ precludes sub-group analysis.

16. Data Analysis Plan

To address the primary aim, weight loss will be analyzed as mean percent of baseline weight loss at months 6, 12, 18 and 24 in the context of linear mixed (fixed and random) effects multi-level models. In addition to intervention group, clinics and assessment time, and their interaction terms, the model may include and patient-level (weight, age, sex, race) and clinic-level (clinic size, %African American, % Medicaid/Medicare, etc.) variables as explanatory covariates.

Preliminary analytical findings will be used to choose the most plausible and efficient repeated measures covariance structure (e.g., compound symmetric, autoregressive, unstructured) to use. Although substantial effort will be employed to minimize missing data, it is inevitable that some missing data will occur. An intention-to-treat analysis that includes all randomized patients, regardless of the number of assessments obtained, will be conducted. The primary analysis will use the mixed effects model mentioned above and employ restricted maximum likelihood using all available data. The analytical plans are flexible and will be adapted as scientific perspectives are advanced.

Additional analyses to test the secondary aims are described below:

Secondary Aim 1. Evaluate relationships between adherence to intervention components (physical activity, diet, sessions, etc.) and corresponding changes in body weight and secondary outcomes (post-hoc analyses).

The first secondary aim will be accomplished by conducting analyses of adherence data and changes in the outcomes, and by conducting sub-analyses in different compliant groups (attended at $\geq 80\%$ of sessions, etc.).

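### The only model stated for quality of life, functional capacity and co-morbidities has no term for clinics differing in change, so its arm comparison may be too liberal or not estimable

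*Combined protocol and SAP*

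**What the plan says.** - **Design.** Section 9 randomises clinics, stratified by health system, and "enrolled patients at a given clinic will receive the intervention assigned to their clinic".
- **General model.** Section 2 (Technical Abstract, Analytic Methods) describes a linear mixed model for continuous outcomes "including the fixed effects of intervention, time, and their 2-factor interactions, with age, sex and clinic as covariates". It then says "Estimated within-group changes between baseline and 6 to 24 months will be estimated and compared using contrasts within the mixed models". The next sentence adds the baseline value of the outcome to the models as a covariate. Dichotomous outcomes get a logit mixed model built the same way. No random clinic term and no clinic-by-time term is named.
- **Weight model.** Section 16 specifies a multi-level model with fixed and random effects for percent weight loss at months 6, 12, 18 and 24. Its terms are introduced with "In addition to intervention group, clinics and assessment time, and their interaction terms". The same section gives Secondary Aim 2 (system-level practices and satisfaction with care) a strategy similar to that of the primary aim.
- **Other hypothesis 2 outcomes.** Section 16 gives no model for quality of life, functional capacity or the co-morbidities.
- **Sample size.** Section 15 recognises clustering of weight change: "After accounting for the design effect, at least 134 patients per arm are required to realize 80% power in a trial randomized at the clinic". No ICC is stated for any outcome.

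**The concern.** In a trial that randomises clinics, the arm comparison has to be judged against how much clinics differ from one another in the quantity compared. Here that quantity is change from baseline. Clinics can differ in change because of the coach, the practitioner team or local circumstances. The Technical Abstract model has nowhere to put such differences: clinic sits beside age and sex and does not vary by visit.

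Two failures are possible, depending on how the model is read. Differences between clinics in change may fall into the patient-level residual, so that intervals are too narrow and ordinary clinic variation can pass as benefit. Or the intervention effect may be impossible to separate from clinic. At stake are outcomes that Section 4 places under the primary aim, as hypothesis 2.

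**Working it through.** **Inputs.** From Section 15: "Power calculations used a nominal 0.05 significance level with a two-tailed test with minimal power of 80" percent; "the standard deviation for weight change for patients nested within clinics was 8.4" percent; and "a net sample size of 184 patients (92/arm) is sufficient for detecting a 3.5% weight loss with 80% power". Also from Section 15: 134 per arm after the design effect, 192 per arm after 30% attrition, 18 clinics, 47 patients per clinic, and at least 97% power with 768 patients. Assumed: 9 clinics per arm.

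**1. The plan's own figures.** n per arm = 2(1.960 + 0.842)² × (8.4/3.5)² = 2 × 7.85 × 5.76 = 90.4, so 91 against 92 stated. 134/0.70 = 191.4, so 192 as stated. Both agree.

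**2. Implied ICC for weight change.** The design effect is 134/92 = 1.457. From DE = 1 + (m − 1) × ICC, ICC = 0.457/(m − 1). The plan does not say which m was used:

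| m per clinic | ICC |
|---|---|
| 134/9 = 14.9 | 0.033 |
| 192/9 = 21.3 | 0.0225 |
| 47 × 0.70 = 32.9 | 0.014 |
| 47 | 0.010 |

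The 97% power gives a second route. The effective n per arm is 2 × [8.4 × (1.960 + 1.881)/3.5]² = 169.9. The net n per arm is 768 × 0.70/2 = 268.8, or 29.9 per clinic. So DE = 268.8/169.9 = 1.582 and ICC = 0.582/28.9 = 0.020.

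**3. Reading A: baseline is one of the responses.** A clinic effect that is the same at every visit, fixed or random, subtracts out of follow-up minus baseline. The contrast then has a patient-level standard error, while its true variance is larger by DE. The actual two-sided error is 2[1 − Φ(1.96/√DE)]. With 33 completers per clinic:

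| ICC | DE | Actual error |
|---|---|---|
| 0.010 | 1.32 | 8.8% |
| 0.020 | 1.64 | 12.6% |
| 0.0225 | 1.72 | 13.5% |
| 0.033 | 2.05 | 17.1% |

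Simulated patient-level tests of change (18 clinics, no true effect, 4,000 runs) rejected 9.0%, 12.4% and 16.0% at ICC 0.01, 0.02 and 0.033. A test on clinic means with 16 degrees of freedom rejected 4.2–5.5%. A direct fit with arm, time, their interaction, a random clinic intercept and a patient effect rejected 13% at ICC 0.033 (300 runs, Monte Carlo SE about 2 points). That is lower and less precise than the formula, but well above 5%.

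**4. Reading B: only follow-up values are responses, baseline is a covariate, clinic is fixed.** Every patient in a clinic has the same arm. Eighteen clinic indicators plus one arm column make 19 columns of rank 18, so the intervention effect cannot be estimated.

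**5. Reading C: as B, but clinic is random.** The clinic effect does not cancel. Simulated error was about 5.7% at ICC 0.033 with 33 per clinic (600 runs, Monte Carlo SE about 1 point, some convergence warnings).

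**The case against.** The best defence has four parts.

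- **Baseline as covariate.** The sentence after the change contrasts makes baseline a covariate. If the follow-up values alone are the response, a random clinic intercept does not cancel and the test is sound. This stands. A reader might infer that declaring clinic random can never cure the problem; the documents do not support that, because it does so under reading C. But reading C needs two statements that the Technical Abstract does not make: that clinic is random, and that baseline is not a response. Contrasts between baseline and later visits within the model, and clinic listed beside age and sex, both point the other way.
- **An abstract is a summary.** Section 16 uses a multi-level model where it elaborates, and it opens by addressing the primary aim, which includes hypothesis 2. That intent is plausible. The model sentence names only weight loss, though, and nothing carries it to these outcomes.
- **Scope.** A reader might take all hypothesis 2 outcomes to be affected. Satisfaction with care is not, because Secondary Aim 2 follows the primary strategy. Percent weight loss has its own Section 16 model and is outside this point.
- **Size.** A reader might infer error rates up to 22%. That needs ICC 0.033 with 47 analysed per clinic and no attrition (21.6%), or ICC 0.05, which exceeds every value derived from the plan. The plan allows for 30% attrition. ICC 0.033 would also give 93.3% power for 768 patients net of attrition, not 97%.

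It is also fair that the Technical Abstract calls the secondary outcomes preliminary and that the sample size does not rest on them. This limits the consequence but does not supply the missing term.

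**Conclusion.** The point holds for quality of life, functional capacity and the co-morbidities. The only model stated for them has no between-clinic variation in change, and it does not say whether baseline is a response, a covariate or both.

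- If baseline is a response, the error rate is about 9–17% at nominal 5%, and about 13% at the ICC consistent with the stated 97% power.
- If baseline is only a covariate and clinic is fixed, the intervention effect cannot be estimated.
- If only follow-up values are responses and clinic is random, the rate stays near 5%, but this model is not written down.

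The percentages assume 9 clinics per arm, 33 completers in each, and outcomes that cluster as much as weight change does. The documents give no ICC for these outcomes, so the range illustrates the size of the problem and is not a measured rate. The logit model shares the structure, but its error rate was not simulated. This should be settled before analysis; it does not call the weight analysis into question.

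**What to change.** For these outcomes, continuous and dichotomous, replace clinic as a covariate with the Section 16 multi-level structure, and state that the clinic terms are random. Choose one form and write it down:

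1. Model the follow-up visits only, with baseline as a covariate and a random clinic effect that may differ by visit; or
2. Keep baseline as a response and add a random clinic-by-visit effect beside the random clinic effect.

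Test the intervention contrast with between-clinic degrees of freedom: 18 − 2 = 16, or fewer if the health-system strata are in the model.

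The cost is SAP wording and added random terms, with no new patients or data. The downside is wider, correct confidence intervals for these outcomes.

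### For the hypothesis 2 outcomes that Section 16 does not model, the abstract's model read literally uses baseline as both response and covariate, so the adjustment gains no precision

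*Combined protocol and SAP*

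**What the plan says.** The Technical Abstract, under Analytic Methods, gives a linear mixed model for continuous outcomes, "including the fixed effects of intervention, time, and their 2-factor interactions, with age, sex and clinic as covariates". Two sentences then deal with baseline. The first: "Estimated within-group changes between baseline and 6 to 24 months will be estimated and compared using contrasts within the mixed models". The second: "Baseline outcomes will further be included in the models as covariates to determine the change in outcome from baseline". Dichotomous outcomes get a logit-link mixed model built in the same way. The abstract names no baseline-by-time term and no covariance structure.

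Section 16 (Data Analysis Plan) treats weight differently: "weight loss will be analyzed as mean percent of baseline weight loss at months 6, 12, 18 and 24". Baseline is not a response there, and it is an optional covariate: "the model may include and patient-level (weight, age, sex, race"). The covariance is to be chosen from preliminary findings: "repeated measures covariance structure (e.g., compound symmetric, autoregressive, unstructured) to use". Estimation is to "employ restricted maximum likelihood using all available data".

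Hypothesis 2 of the primary aim (Section 4) covers quality of life, functional capacity, satisfaction with care and co-morbidities. Section 16 handles satisfaction under Secondary Aim 2, by a strategy like that of the primary aim. It writes out no model for the other three.

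**The concern.** A change from baseline can be a contrast within a model only if baseline is one of the modelled visits. Adding the same value as a covariate puts it on both sides of the equation. Two things follow. First, an adjustment meant to gain precision may gain none. Second, in the baseline row the response equals its own covariate, which can make the likelihood degenerate if that visit has its own variance.

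At stake are precision, convergence and analyst discretion for quality of life, functional capacity and co-morbidities, where the analyst has no other model to follow.

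**Working it through.** **Inputs.** The model terms come from the Technical Abstract, and the covariance options and weight model from Section 16. The baseline-to-follow-up correlation rho is not given in the documents, so a range is assumed. The plan states no figure for this point. The design effect used in step 4 rests on two Section 15 figures, which were checked first. With a difference of 3.5, SD 8.4, two-sided 0.05 and 80% power, the formula gives 91 per arm (normal) or 91.4, so 92 (t-test), against 92 stated. Attrition: 134/(1 − 0.30) = 191.4, so 192, as stated.

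**Step 1, cancellation in the linear model.** Let the mean at visit t be mu_t + b·y0, with one slope b for all visits including baseline. Then

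(mu_t + b·y0) − (mu_0 + b·y0) = mu_t − mu_0.

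The covariate has gone. This was checked on one simulated complete data set (18 clinics of 47, so n = 846; baseline plus four visits; all parameters assumed; age, sex and clinic terms left out of the fit). Under compound symmetry, the month-24 between-arm change contrast was:

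| Analysis | Estimate | SE |
|---|---|---|
| Baseline as response, no covariate | −5.2546 | 0.4258 |
| Baseline as response and covariate | −5.2546 | 0.4258 |
| Raw difference in change scores | −5.2546 | |
| Month 24 adjusted for baseline (ANCOVA) | −5.0247 | |

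The first three agree. One data set shows that identity; it does not show which estimator is nearer the truth.

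**Step 2, precision.** On the outcome's own scale, with equal variances at both visits, the change score has variance proportional to 2(1 − rho) and the baseline-adjusted analysis 1 − rho². The ratio is 2(1 − rho)/(1 − rho²) = 2/(1 + rho).

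| Assumed rho | 2/(1+rho) |
|---|---|
| 0.3 | 1.54 |
| 0.5 | 1.33 |
| 0.7 | 1.18 |
| 0.9 | 1.05 |

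**Step 3, degeneracy.** At slope 1 every baseline residual is zero. If the baseline visit has its own variance s, the log-likelihood contains −(n/2)·ln(s), which rises without limit as s goes to 0. From s = 1 to s = 0.01 the rise should be 423 × ln(100) = 1948; the computed values went from −11178.7 to −9230.7, a rise of 1948.0. Iterating the unstructured fit took the slope from 0.938 to 0.999999, the baseline variance from 1.04 to 3e-10 and the log-likelihood from −13557 to −4229, still climbing. The arm contrast stayed at −5.2546. Under compound symmetry the log-likelihood was finite (−12995).

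**Step 4, clinic variance.** As an illustration, borrow the Section 15 design effect, 134/92 = 1.457, and treat it roughly as a patient part of 1 plus a clinic part of 0.457 that baseline adjustment leaves alone. The ratio becomes 1.457/[(1 + rho)/2 + 0.457]:

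- rho 0.3: 1.457/1.107 = 1.32
- rho 0.5: 1.457/1.207 = 1.21
- rho 0.7: 1.457/1.307 = 1.11
- rho 0.9: 1.457/1.407 = 1.04

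This design effect belongs to weight change in a subgroup, so for other outcomes it is only indicative.

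**Step 5, the Section 16 form.** With percent change at the four post-baseline visits and baseline weight as covariate, the unstructured fit was regular: log-likelihood −10377, smallest eigenvalue 14.6, condition number 9.8. The covariate did enter the month-24 effect (−5.00 with it, −5.20 without).

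**Step 6, the logit version.** The cancellation in step 1 is a linear-model result. In 25 simulated trials (425 per arm, no clinic effect, assumed parameters), including the baseline row raised the baseline slope from 2.04 to 2.61 and cut the random-intercept SD from 1.40 to 1.04. The mean contrast barely moved (−0.75 versus −0.72). Its empirical SD went from 0.204 to 0.229, but 25 replicates are too few to lean on that difference.

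**The case against.** The strongest reply is that the abstract never lists baseline as a response visit. It defines outcomes as changes ("The primary outcome is percent change in body weight from baseline", with the secondary outcomes framed as changes too). So its sentences could describe a model of change at months 6 to 24 adjusted for baseline, which is regular. For continuous outcomes that reading is possible. It fits the dichotomous outcomes poorly: a binary outcome has no change score to place under a logit link, so a within-model change needs baseline as a response, and the abstract uses one approach for both types. The literal double use is therefore the natural reading, though not the only one.

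Other parts of the reply stand:

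- The unstructured matrix is named only in Section 16, as one of three examples, for a model with no baseline row. Degeneracy arises only if that option is carried over to the abstract's model, and a fit that does not converge need not be kept.
- Cancellation assumes a common slope, and it is numerically exact only with complete data. The abstract neither names nor excludes baseline-by-time, and the plan allows for 30% attrition.
- The factor 2/(1+rho) is a patient-level figure at assumed correlations; at 0.9 it is 5%.
- The abstract is not the only source for every secondary outcome, because Section 16 covers satisfaction.

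**Conclusion.** The point holds for quality of life, functional capacity and co-morbidities. For these, the abstract's model followed literally gives baseline two roles. In the linear model the stated adjustment then gains nothing, and the result is the unadjusted change-score comparison. The loss is in variance: 1.05 to 1.54 times at patient level for rho from 0.9 down to 0.3, and about 1.04 to 1.32 times with the borrowed design effect. These sizes rest on assumed correlations, equal variances, a common slope and complete data. A degenerate fit is a further risk only if visit-specific baseline variance is allowed.

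A reader might infer more, and the documents do not support it:

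- *The primary weight analysis breaks down.* Section 16 models months 6 to 24 only and is regular. Abstract and Section 16 differ on whether the baseline covariate is included or optional, but that is a matter for alignment.
- *The treatment effect would be biased.* The change-score contrast is valid, and it did not move even in the degenerate fit. No bias was shown in the logit version.
- *The models will fail to converge.* Compound symmetry stays bounded.

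This is a free improvement, not a flaw in the primary result.

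**What to change.** For these continuous and dichotomous outcomes, state one model: responses at the post-baseline visits at which each outcome is measured (Table 2); fixed effects for arm, visit, arm-by-visit, baseline value and baseline-by-visit; a random clinic effect; and the arm contrast at month 24. Use the logit link for dichotomous outcomes, again with post-baseline rows only. Put this in Section 16 and reword the abstract so that both give baseline the same role.

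Merely dropping the covariate and keeping baseline as a response would be coherent, but it would not recover the precision: in step 1 the contrast and its SE were the same with and without the covariate.

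The cost is wording in the abstract and Section 16. It needs no new data and loses no power.
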